#### **B. INNOVATION**

Our proposed research is innovative for several reasons:

- 1. We focus on a patient population (those with HF) with unique issues e.g., symptom burden, impaired cognition, frequent hospitalizations, multimorbidity, and complex regimens that increase caregiver demand, burden, and stress. While dementia caregivers face many of these issues,  HF is different because palliative care is not offered routinely and respite services are rarely available.  Without support services, these caregivers are extraordinarily stressed.  High stress levels are associated with poor self-care. 
- Few studies of caregivers have focused on their self-care, and those studied other populations. Most studies of HF emphasize the caregiver's role in promoting HF patient self-care. The proposed study will provide a robust description of HF caregivers' self-care and the manner in which it changes with intervention.
- 3. We have developed a unique approach to health coaching that targets stress and self-care concurrently. ViCCY is potentially more powerful than interventions addressing either issue alone because self-care is lower in stressed populations and self-care can potentiate stress reduction approaches.
- 4. Using video technology to intervene with caregivers is *not* new but it is new in HF caregivers, who are a predominately older population. In spite of mounting evidence that older adults use technology regularly,  ageism persists and elders often are assumed to be unable to participate in research using technology.  Our proposed study will be one of the first adequately powered trials of a virtual intervention for predominately older caregivers. If efficacious, this approach to the delivery of ViCCY can easily be deployed in any location and with other populations.
- 5. Very few caregiver intervention studies have addressed cost-effectiveness. We include a formal cost effectiveness analysis in which caregivers are followed for 12 months.
- 6. We explore the influence of caregiver outcomes on HF patient outcomes. A growing body of research illustrates the powerful influence of individuals in a dyad or couple on each other.  But our study is unique and innovative in exploring the effect of a stress intervention for caregivers on outcomes in HF patients. Measuring QALYs in both caregivers and HF patients, we will be able to assess benefit in both.

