- Aim 2: To estimate the cost and cost-effectiveness of ViCCY. We hypothesize that, at 12 months after enrollment, caregivers randomized to ViCCY vs. HI alone will have **H2a**: Higher QALYs measured with the SF-6D (short form six-dimension) derived from the SF-36 (secondary outcome); and **H2b**: Lower health care resource use (secondary outcome).
- Aim 3 (Exploratory): To explore the effect of caregiver outcomes on HF patient outcomes. We hypothesize that, at 12 months after enrollment, HF patients whose caregivers improve vs. not improve in self-care regardless of group will have **H3a**: Lower hospitalization rates; **H3b**: Fewer hospital days; **H3c**: Lower mortality rates; and **H3d**: Higher QALYs measured with the SF-6D.

If shown to be efficacious and cost-effective, our virtual health coaching intervention can easily scaled to support millions of caregivers worldwide. This application addresses the NINR strategic plan and is directly responsive to PA-18-150.

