**C.14.3.** Aim 3 (Exploratory): To explore the effect of caregiver outcomes (self-care, stress, coping, health status) on HF patient outcomes. We hypothesize that at 12 months, HF patients whose caregivers improve vs. not improve in self-care (regardless of group) will have H3a: Lower hospitalization rates; H3b: Fewer hospital days; H3c: Lower mortality rates; and H3d: Higher QALYs measured with the SF-6D. We will analyze number of hospitalizations and days in the hospital using GEE regression models with the Poisson distribution as the working outcome distribution. GEE allows for modeling of the marginal distribution of each outcome variable as a function of the caregiver predictor of interest over time, and accounts for the likely correlations of the repeated outcome measures for each participant. An approach similar to that described for Aim 1 will be used within the GEE framework (different correlation structures will be examined, baseline outcomes will be included as a covariate).

We will measure time to death from date of the caregiver's enrollment in the study to the date of patient death. Patients remaining free from an event will be censored at their last follow-up. Kaplan-Meier estimates will be plotted to provide a visual demonstration of time to death by group (categorized caregiver outcomes), and the log-rank test will be used for comparisons. GEE and frailty type multivariable modeling will be applied to time-to-event data within the context of equally spaced time intervals. This approach allows for the addition of a random effect to a general Cox proportional hazards model to account for the likely correlation of repeated measures for each study participant while also accounting for censoring.

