## **C.15. Methodological challenges.** We have considered the following methodological challenges:

- 1. There is the possibility of differential compliance with the protocol for instance, if the HF patient has an exacerbation that distracts the caregiver and interferes with the intervention or assessments. We will allow some flexibility in the timing of ViCCY sessions to accommodate such events and increase the generalizability of study results. Caregivers in the ViCCY arm will be able to schedule calls with the RN coach during day, evening, and weekend hours to limit stress from study participation. For both arms, we will allow data collection calls to be completed up to two weeks before or after the planned contact date to accommodate schedules. We will collect data on cancelled and delayed events for later analysis and adjust for delays and the dose of intervention received in analyses.
- 2. A threat to validity includes the potential for the control group to receive a level of natural support sufficient to interfere with our ability to detect treatment effects from ViCCY. We will interview participants about naturally occurring support so that we can adjust for this in the analysis if needed.
- 3. We may have difficulty enrolling the most stressed and burdened caregivers who may see the trial as one more demand; however, in pilot testing we found that caregivers were grateful for the support.
- 4. It is possible that the patient could die during the year in the study; half of all HF patients die within 5 years. 11 Should this occur, the caregiver will be dropped from the study.

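### Exploratory Aim 3 relates patient outcomes only to caregiver outcomes after randomisation, so it cannot support the Innovation statement about the intervention's effect on HF patients; a descriptive comparison by arm would be a cheap addition

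*Combined protocol and SAP*

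**What the plan says.** Section B, item 6, makes two kinds of statement. It opens with the narrower one, "We explore the influence of caregiver outcomes on HF patient outcomes". It then says that "our study is unique and innovative in exploring the effect of a stress intervention for caregivers on outcomes in HF patients", and adds "Measuring QALYs in both caregivers and HF patients, we will be able to assess benefit in both". Section A.6 supplies the motive: it reports that no earlier study has tested how an intervention for caregivers affects HF patient outcomes.

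The Specific Aims and C.14.3 define the patient hypotheses H3a to H3d (hospitalisation rates, hospital days, mortality, QALYs) by caregiver change: "HF patients whose caregivers improve vs. not improve in self-care (regardless of group) will have" the better outcome. Hospitalisations and hospital days are modelled "as a function of the caregiver predictor of interest over time". Survival curves are drawn by categories of caregiver outcome. The patient QALY model uses time-dependent caregiver variables, time and their interaction. The Actor-Partner model also takes caregiver outcome as its predictor. Aim 3 is labelled exploratory, and C.14.3 says its findings will serve to generate hypotheses.

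**The concern.** Caregivers are randomised 1:1, so patients of ViCCY caregivers and patients of HI caregivers form groups created by chance. No section compares patient outcomes between those groups. The groups that are compared, or the predictors that are used, come into being during follow-up and can themselves result from how the patient is doing.

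If patients of improving caregivers had fewer admissions, item 6 would invite the reading that the intervention helped patients. The same result could arise if stable patients simply leave their caregivers freer to improve. The analysis that separates the two explanations uses data already being collected, but is not planned.

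**Working it through.** **Which patient analyses use the randomised arm?**

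| Patient outcome | Planned analysis | Predictor or grouping | Arm included? |
|---|---|---|---|
| Hospitalisations, hospital days | Poisson GEE (C.14.3) | Caregiver predictor | No |
| Death | Kaplan-Meier, log-rank, frailty model (C.14.3) | Categorised caregiver outcome | No |
| QALYs (SF-6D) | Mixed model (C.14.3) | Time-dependent caregiver variables × time | No |
| Dyadic analysis | Actor-Partner model (C.14.3) | Caregiver outcome | No |

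The randomised QALY comparison in C.14.2 concerns caregivers. The Human Subjects section mentions patients by study group only to allow comorbidity as a covariate.

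**Do the documents describe influence running from patient to caregiver?** Yes, in three places. Section A.2 reports that patient hospitalisations are very stressful for caregivers. The scientific premise under A.7 says dyadic influence runs in both directions. C.15, item 1, anticipates differential compliance "if the HF patient has an exacerbation that distracts the caregiver and interferes with the intervention or assessments". C.14.3 sets no rule that caregiver change must precede the patient events it is related to.

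**How large could the resulting association be?** The documents give no patient event rates, so every input here is assumed. Let hospitalisations be Poisson with mean 1 per year (0.5 per half-year), with no effect of caregiver on patient. Let the caregiver's chance of improving by month 6 be 60% with no hospitalisation in months 0–6 and 40% otherwise.

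- P(at least one in months 0–6) = 1 − exp(−0.5) = 0.393; mean given at least one = 0.5/0.393 = 1.27.
- P(improve) = 0.6 × 0.607 + 0.4 × 0.393 = 0.521.
- P(hospitalised | improved) = 0.4 × 0.393/0.521 = 0.302; P(hospitalised | not improved) = 0.6 × 0.393/0.479 = 0.493.
- 12-month mean, improvers: 0.302 × 1.27 + 0.5 = 0.884; non-improvers: 0.493 × 1.27 + 0.5 = 1.127.
- Crude rate ratio = 0.884/1.127 = 0.78, when the true causal ratio is 1.00.

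Varying the rate from 0.5 to 1.5 per year and the chance of improving after a hospitalisation from 30% to 50% gives about 0.63 to 0.91. A separate simulation used a different mechanism: an unmeasured factor shared by caregiver and patient, with assumed loadings of 0.3 to 0.5. Improver and non-improver patients then differed by 0.14 to 0.39 SD, while the arm difference was zero.

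**How precise would a comparison by arm be?** C.4.a plans at least 40 dyads; 1:1 allocation suggests about 20 per arm.

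- Continuous outcome: 95% half-width = t(0.975, 38) × √(2/20) = 2.024 × 0.316 = 0.64 SD.
- Difference detectable with 80% power, two-sided 0.05: (1.960 + 0.842) × √(2/20) = 0.89 SD.
- Hospitalisations at the assumed 1 per year (20 events per arm, no overdispersion or loss): exp(±1.96 × √(1/20 + 1/20)), so an interval of about 0.54 to 1.86 around a rate ratio of 1.00.

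**The case against.** The strongest reply is that aim and analysis agree. Aim 3 is consistently framed as the effect of caregiver outcomes, item 6 opens that way, and H3a to H3d and their models follow it. No aim or hypothesis promises a ViCCY versus HI comparison in patients, and the exploratory label limits what will be claimed. On this view one sentence in the Innovation section is loose and a wording change suffices. Pooling the arms is also a defensible way to study caregiver change in so few dyads.

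Most of that stands. A reader might infer that the plan contradicts its own aim, or that improvement status is the only patient comparison; the documents support neither. C.14.3 also names caregiver stress, coping and health status. These share the weakness, because they too are measured after randomisation. The statement about benefit is supported for caregivers by the randomised comparison in Aim 2; the gap is on the patient side.

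The illustrative 0.78 must not be read as the bias of the planned models. It is a crude ratio with improvement fixed at month 6, whereas the hypotheses refer to 12 months. The plan also includes baseline patient outcomes, patient comorbidity and time-dependent caregiver variables. Those covariates would not remove reverse causation from events during follow-up.

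The objection falls short on one point. An exploratory label does not remove bias, and C.14.3 still declares significance at a two-sided 0.05 level. C.14 also says all analyses follow intention to treat, which a comparison pooled by caregiver improvement does not.

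**Conclusion.** The Aim 3 analyses can describe how caregiver change and patient outcomes go together. They cannot support a statement about the effect of ViCCY on patients. That follows from the text and rests on no assumed figure. The size of the possible bias is unknown; 0.63 to 0.91 for a crude rate ratio shows only that a visible association can arise with no effect.

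A reader might also infer that a comparison by arm would settle whether ViCCY benefits patients. It would not: at the planned minimum its interval for hospitalisations (0.54 to 1.86 under the assumed rate) is wider than the whole illustrated range of bias. Its value is that it is the only randomised evidence the trial can give on the point item 6 calls innovative. This is a low-cost improvement to an exploratory aim. Aims 1 and 2 are unaffected.

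**What to change.** 1. In C.14.3, add a descriptive comparison by the caregiver's randomised arm for patient hospitalisations, hospital days, death and SF-6D, given as estimates with 95% confidence intervals. State that about 20 dyads per arm gives wide intervals and that no efficacy conclusion will be drawn.
2. Define the set as patients who consented before their caregiver was randomised, or report consent timing by arm. The documents do not state this order explicitly.
3. Keep patients in this analysis through the EMR if the caregiver leaves the study. Reconcile this with C.15, item 4, which drops the caregiver when the patient dies, and with C.11, where caregivers report patient admissions outside the Penn system. Also reconcile C.10 (patient SF-6D at baseline and 12 months) with the Recruitment and Retention Plan, which mentions only the end of the study.
4. Keep the caregiver-outcome analyses, described as associations, with arm as a covariate and the caregiver score measured before the period in which patient events are counted.
5. Limit the wording of item 6 in section B to match.

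The cost is a few sentences and one exploratory table. Arm and the patient outcomes are already to be recorded; consent dates are the only item that may need adding.

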#### C. APPROACH

- **C.1.** Research Team (see Biographical Sketches and Letters of Support for details). Our multidisciplinary team based at the University of Pennsylvania (Penn) is well positioned to complete the proposed study. Team members, most of whom have worked together for the past decade,  bring unique but complementary perspectives that have informed all dimensions of the proposal: [name] [Principal Investigator (PI)] HF, health coaching, motivational interviewing, caregivers, self-care]; [name] (Co-I) virtual technologies; [name] (Co-I) interventions with older caregivers; [name], DO (Co-I), heart failure; [name] (Co-I) cost-effectiveness analysis; and [name] (Co-I) biostatistics. Led by the PI, members will share responsibility for the conduct and integrity of the study. See Budget Narrative for specific responsibilities and contributions.
- **C.2. Preliminary Studies**. We developed our intervention in patients and have modified it for caregivers. In the first study, we *refined our tailored health coaching intervention in 15 HF patients* (mean age  $60 \pm 13.3$  years, 53% White, 60% female). The intervention, provided by an RN during an average of  $3 \pm 1.5$  home visits over 3 months, focused on improving self-care. Motivational interviewing was used to elicit beliefs about the illness, personal goals, and self-efficacy. Reflective listening and empathy were used to provide support, decrease barriers and build skill in self-care. There was evidence of improvement in self-care in 80% of HF patients after receiving the intervention. In a second study, we tested health coaching vs. standard education in 100 HF patients (mean age  $62 \pm 12.8$  years, 54% Black, 30% female) in an RCT. The intervention was provided by an RN in 1 in-person session and 2-3 telephone sessions over the first month after hospital discharge. At 3 months, more improvement in self-care was seen on the Self-Care of HF Index 148

in the intervention group than the control group (19.7  $\pm$  16.0 vs. 12.1  $\pm$  18.3 improvement in standardized scores), a clinically and statistically significant difference after adjusting for confounding variables. The effect size was moderate (Cohen's d = 0.44). Based on qualitative data collected in both studies, we learned that face-to-face sessions were more effective than telephone sessions, so we moved to using virtual technology.

In preparation for this proposal, we conducted three pilot studies to adapt the intervention for caregivers. We first enrolled seven homebound female spouse caregivers of HF patients and interviewed them to identify stressors associated with caregiving. When we described the planned program, all were receptive to the electronic intervention and five of the seven women wanted to participate ("I need help desperately"). 71 In the second pilot study, we tested four methods of distance communication – telephone, tablet (iPad) with video, laptop computer with video and a detachable webcam, and touchscreen videophone. The iPad facilitated privacy by allowing the caregiver to move to a private place while conversing and was preferred over other devices ("the iPad is just less threatening"). In the third study, we assessed feasibility of our planned methods and pilot-tested the ViCCY intervention. 150 We enrolled four HF caregivers (white female spouses, mean age 66 ± 8.5 years) and gave each an iPad. Health coaches engaged each caregiver in 8 support sessions over a 3-month period. Each session lasted approximately 1 hour. Data were collected at enrollment and three months later using most of the methods proposed below. Table 1 shows change in the main target variables. Technology problems were more common in coaches than caregivers and were quickly resolved with assistance. Together these pilot studies illustrate that caregivers are interested in participating, they are comfortable with the tablet technology, and our proposed methods are feasible. We learned to hire coaches adept with technology and to ensure that participants have a strong Internet connection.

Table 1. Results from Pilot Study of Four Caregivers	Baseline Score (SD)	3-Month Follow-up Score (SD)
Perceived Stress Scale (lower is better)	20.7 (4.3)	18.2 (0.96)
Health Self-Care Neglect Scale (1-10 possible range, lower is better)	3.2 (2.5)	1.2 (1.2)
SF-12 Health Status, Mental Component Score (higher is better)	52.1 (9.1)	55.6 (4.3)

We have used virtual technology to deliver numerous interventions, including some of the early work using virtual approaches with older adults.  In a field experiment funded by the Department of Commerce, we enrolled 174 elderly diabetic home health patients and provided a virtual intervention.  Of those who refused, only 12% said the technology was too complicated, in spite of the fact that we used first-generation technology that was far more complicated than that proposed in this study – a virtual technology approach with tablets. Satisfaction with this delivery method was high. Our research staff has extensive experience in setting it up and instructing those having no knowledge of tablets to become proficient in its use. 

**C.3. Study Overview (Figure 2).** We will use a RCT design to achieve robust and unbiased results, as detailed below. We will enroll 250 informal HF caregivers and, when possible, the HF patients for whom they care. After collecting baseline data, we will block randomize the caregivers 1:1 to the intervention or control group, stratifying randomization by caregiver sex and relationship to the patient (e.g., spouse, adult child) –

factors known to influence caregiving burden, perceived stress, and receptivity to the intervention. We will provide tablet devices with wireless network access and connect caregivers in both conditions to the Internet so they can access the Internet site providing Health Information (HI) content, which will be the only content provided to caregivers in the control group. In addition to HI, the intervention group will receive 10 front-loaded sessions of

**Figure 2.** Illustration of the sequence of enrollment, randomization, and data collection over the 12 month period. Data collection time point months shown in **bold**. Primary outcome collected at 6-months. (R=randomization)

ViCCY over 6 months. Assessments of self-care, perceived stress, coping, and health status will be conducted at baseline (after enrollment but prior to randomization) and by phone at 3, 6, 9 and 12 months. Using contrasts within a mixed-effect modeling framework, we will assess intervention efficacy at 6 months using intention-to-treat analysis. We chose to provide 10 health coaching sessions based on our pilot data and literature demonstrating that a shorter duration of health coaching is not routinely effective. Ye chose to assess the primary aim at 6 months based on prior psychosocial intervention studies, \$3,125,155 but we will assess outcomes at 3-month intervals based on this rationale: baseline (enrollment), to generate consistent profiles of all enrollees at a consistent point in time and prior to implementation of the new intervention; at 3-months, very early effects, at 6-months, short-term effects; and at 12-months, the longer-term effects of ViCCY vs. HI. These 3-month intervals also will allow us to compare our results with others. Ye chose a 12-

month follow-up interval for the cost-effectiveness analysis to allow for a full year of event accrual. We will pull resource use data from the electronic medical record (EMR) in 30 day increments and validated these data during routine follow-up calls with caregivers. We expect the proposed study to require 5 years for completion.

#### C.4. Sample.

**C.4.a Recruitment.** We will enroll a consecutive sample of informal HF caregivers identified from the Penn Heart and Vascular Center (PHVC), the largest out-patient HF clinic in the Philadelphia region and a site at which the PI has established relationships and success in past recruitment of participants. In 2017, there were 5344 HF patient visits (mean 445 visits per month). Of these, approximately 832 were new HF patients (mean 69 new patients per month). In a prior study at this site, we enrolled 139 HF patients over 18 months; 84% of the screened and eligible patients enrolled. These 139 HF patients (45% female, 34% non-White, mostly Black) all lived at home with a family caregiver.

If recruitment is slower than expected, we will identify caregivers visiting HF patients hospitalized at one of three University of Pennsylvania Health System (UPHS) sites, all of which use a single, integrated EMR with the level of financial data needed to address our cost-effectiveness aim. The Hospital of the University of Pennsylvania (HUP) has 789 licensed acute care beds. Between July 2016 and July 2017, HUP admitted 1,859 HF patients. Presbyterian Medical Center (PMC) has 331 patient beds and admitted 1,621 HF patients in that year. Pennsylvania Hospital (PAH) has 496 licensed patient beds and admitted 716 HF patients that year. From these various sources, it is reasonable to project identifying **100 unique HF patients each month**, most of whom will have caregivers. Based on our prior research, 158-161 we anticipate that 90 will have caregivers and 70% of these (63 caregivers) will be eligible, and 15% will enroll. Thus, we estimate enrolling 10 caregivers per month. We will require a minimum of 25 months for enrollment, and have conservatively allowed 30 months for enrollment and five years to complete the study.

